Indirect muscle injuries (IMIs) are a considerable burden to elite football (soccer) teams and prevention of these injuries offers many benefits. Preseason medical, musculoskeletal and performance screening (termed periodic health examination (PHE)) can be used to help determine players at risk of injuries such as IMIs, where identification of PHE-derived prognostic factors (PF) may inform IMI prevention strategies. Furthermore, using several PFs in combination within a multivariable prognostic model may allow individualised IMI risk estimation and specific targeting of prevention strategies, based upon an individual's PF profile. No such models have been developed in elite football and the current IMI prognostic factor evidence is limited. This study aims to: 1) to develop and internally validate a prognostic model for individualised IMI risk prediction within a season in elite footballers, using the extent of the prognostic evidence and clinical reasoning; 2) explore potential PHE-derived PFs associated with IMI outcomes in elite footballers, using available PHE data from a professional team.

METHODS

A retrospective review has been completed of PHE and injury data, routinely collected over 5 years (from 1st July 2013 to 19th May 2018) from a population of elite male players at an English Premier League football club. Of 60 candidate PFs, 15 were excluded. Ten factors will be included in model development that were identified from a systematic review, missing data assessment, measurement reliability evaluation and clinical reasoning. A full multivariable logistic regression model will be fitted, to ensure adjustment before backward elimination. The performance and internal validation of the model will be assessed. The

remaining 35 candidate PFs are eligible for further exploration, using univariable logistic regression to obtain unadjusted risk estimates. Exploratory PFs will be grouped according to type and incorporated into multivariable logistic regression models to determine risk estimates.

DISCUSSION

This study will offer insights into clinical usefulness of a model to predict IMI risk in elite football and highlight the practicalities of model development in this setting. Exploration may identify other relevant PFs for future confirmatory studies, model updating, or influence future injury prevention research.

ABSTRACT WORD COUNT= 342

BACKGROUND

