highlight factors that may be associated with an injury outcome (prognostic factors) and therefore help explain differences in injury risk across individuals within the team (18). Several prognostic factors could also be used in combination within a multivariable prognostic model to predict an individual's absolute injury risk (20, 21). Importantly, both prognostic models and prognostic factors (PFs) can be used inform management approaches designed to modify an individual's absolute risk (21). Despite the potential benefits of prognostic models for shaping injury prevention strategies aimed at clinically important injuries such as IMIs, none have been developed in elite football (22). In addition, there are significant methodological limitations in the evidence base on PHE-derived PFs (22).

Therefore, this study will consist of two primary objectives: 1) to develop and internally validate a prognostic model for individualised IMI risk prediction during a season in elite footballers, using a small number of PHE-derived candidate PFs selected from a previous systematic review (22) and clinical reasoning; 2) to explore potential PFs associated with IMI outcomes during a season in this elite cohort using available PHE data from a professional team.

METHODS

Study Design

This study will be of retrospective cohort design, using a population of male elite football players aged 16-40 years old at an English Premier League club. The first objective will be conducted in accordance with existing guidelines for model development and internal validation (23, 24), and reported in accordance with the Transparent Reporting of a

Multivariable Prediction Model for Individual Prognosis or Diagnosis (TRIPOD) statement (25, 26). The second objective will be conducted in accordance with existing guidelines (27) and reported in accordance with the REporting recommendations for MARKer prognostic studies (28, 29).

Data sources

Both studies will use routinely collected data that was obtained over five seasons (from 1st July 2013 to 19th May 2018). Data collected from the musculoskeletal and performance test components of the club's PHE will be used to identify candidate PFs. Injury outcome data will also be used to establish the available number of IMI outcomes.

Preseason PHE data collection

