As this study will retrospectively utilise the available dataset, a formal sample size calculation has not been conducted, as the total sample size and IMI outcomes are already fixed. To maximise power, we have elected to use all data from the 5-season period. This approach agrees with methodological recommendations that data splitting should be avoided, and all available data should be used for model validation (32).

The number of candidate PFs for inclusion in model development will be restricted to be a minimum of 10 events per variable, which is recommended to reduce overfitting and

optimism during development of a logistic regression model (33). Note that ‘variable’ here means a parameter included (or considered for inclusion) in the model that corresponds to one of the PFs. Although data cleaning for the final season is still in progress, we anticipate that the minimum number of index IMIs will be 100, so will restrict to 10 candidate PFs (variables) for inclusion in the model.

Assuming the model will have a modest R Nagelkerke-squared of 25%, then with an anticipated outcome proportion of 0.381, our 10 events per variable restriction corresponds to targeting an expected shrinkage of 0.85, and thus a relatively small amount of overfitting (15%) (34).

Candidate prognostic factors

A complete list of 60 candidate PFs extracted from the PHE dataset is presented in Table 1.

Table 1: Candidate prognostic factors extracted from PHE data

Type of Prognostic Factor	Candidate Prognostic factor	Measurement method	Data type
Anthropometrics	Age	Date of birth	Continuous
	Height	Standing height measure	Continuous
	Weight	Digital scales	Continuous
	Body fat	Skin callipers	Continuous
	BMI	Composite height (cm) and weight (kg)	Continuous
Medical history	Frequency of previous muscle injuries within 3 years prior to PHE	Medical records	Discrete (treated as continuous)
	Most recent previous muscle injury within 3 years prior to baseline PHE	Medical records	Categorical
	Frequency of previous foot or ankle injuries within 3 years prior to PHE	Medical records	Discrete (continuous)
	Most recent previous foot or ankle injury within 3 years prior to PHE	Medical records	Categorical

	Frequency of previous hip or groin injuries within 3 years prior to PHE	Medical records	Discrete (continuous)
	Most recent previous hip or groin injury within 3 years prior to PHE	Medical records	Categorical

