Discrimination performance is a measure of a model's ability to separate participants who have experienced an outcome compared to those who have not, quantified using the C (concordance) statistic (equivalent to the area under the ROC curve) (23). This index measure will be calculated for the development model, where 1 demonstrates perfect discrimination, while 0.5 indicates that discrimination is no better than by chance alone.

To quantify the degree of optimism due to overfitting, our model will be internally validated using bootstrap re-sampling. This will be conducted as previously outlined (26, 53). The prognostic factor variable selection procedure and model construction will be repeated for 200 bootstrap samples. For each sample, the difference in bootstrap apparent performance (of the bootstrap model in the bootstrap data) and test performance (of the bootstrap model in the original dataset) will be averaged across the 200 samples, to obtain a single estimate of optimism for each performance statistic. Then, to calculate optimism-adjusted estimate of

performance for our new model, the estimates of optimism will be subtracted from the original apparent estimates of performance.

The optimism-adjusted calibration slope will provide a uniform shrinkage factor, which will be applied to all prognostic factor effects in the developed model to adjust (shrink) for overfitting. The intercept of the model will then be re-estimated accordingly. This will then form our final model.

Prognostic factor exploration

All candidate factors eligible for the exploratory study will undergo univariable logistic regression analyses to determine unadjusted associations with IMIs. Candidate PFs will be grouped according to PF type (Table 4) and incorporated into multivariable logistic regression models to determine regression coefficients and odds ratios after adjustment for age, BMI, frequency of previous IMIs and most recent IMI within the 3 years prior to PHE, (which were included as candidates in the original model). During multivariable analysis of the anthropometric candidate factors, BMI will not be included in these models due to collinearity with height and weight factors. Exploration of non-linear associations between candidate factors and index IMI outcomes will be evaluated using a fractional polynomial approach (49). This analysis will allow examination of added prognostic value over and above other factors included in the original model.

DISCUSSION

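### Read as one joint model per factor type, the exploratory medical-history model carries 35 or 46 parameters on about 100 events and contains its own adjuster's components

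*Combined protocol and SAP*

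**What the plan says.** The exploration of prognostic factors is one of two co-equal aims: "this study will consist of two primary objectives". The abstract says of its possible use: "Exploration may identify other relevant PFs for future confirmatory studies, model updating, or influence future injury prevention research".

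On model structure, the Prognostic factor exploration section under Statistical analysis says "Candidate PFs will be grouped according to PF type (Table 4) and incorporated into multivariable logistic regression models", and the abstract says much the same: "Exploratory PFs will be grouped according to type and incorporated into multivariable logistic regression models to determine risk estimates". Estimates are reported "after adjustment for age, BMI, frequency of previous IMIs and most recent IMI within the 3 years prior to PHE". For the anthropometric factors there is one exception: "BMI will not be included in these models due to collinearity with height and weight factors". The section closes by giving the aim as learning what a factor contributes beyond those already in the developed model. Unadjusted estimates are reported for every exploratory factor as well.

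Table 4 lists 35 exploratory factors: 2 anthropometric, 20 medical history, 5 musculoskeletal and 8 strength/power. The medical-history factors are a count and a recency factor for each of ten sites, five of which are muscle groups (iliopsoas, adductor, hamstring, quadriceps, calf). Every recency factor has three bands: under 6, 6 to 12, and over 12 months.

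On size, the Sample Size section says "we anticipate that the minimum number of index IMIs will be 100". It limits model development to 10 events per variable, counting parameters, and links that limit to an expected shrinkage of 0.85.

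**The concern.** Grouping by type and then entering the group in a multivariable model points to one model per group, and dropping BMI because of height and weight fits that. Three of the four groups are then of moderate size. Medical history is not: it has 20 of the 35 factors, half of them categorical.

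The same model would hold five muscle-site counts together with an adjuster that counts all previous muscle injuries over the same three years. The five muscle-site recency factors overlap the recency adjuster in the same way. The plan removes BMI for an analogous reason in the anthropometric group but has no matching rule here.

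At stake are the adjusted odds ratios in the largest exploratory group, which are meant to point to factors for confirmatory work or model updating. An overfitted or singular model could send that work in the wrong direction.

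**Working it through.** **Inputs.** Events 100 (anticipated minimum), outcome proportion 0.381 and Nagelkerke R² 25%, all from Sample Size. Factor counts come from Table 4. Adjusters: age 1, BMI 1 (0 in the anthropometric group), frequency 1, recency 2 (three bands) or 3 (with a level for no prior injury). That is 5 or 6 parameters, or 4 or 5 without BMI. Intercepts and fractional polynomial terms are not counted.

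**The plan's own figure.** Expected shrinkage S solves P = n(S − 1)ln(1 − R²cs/S).
- n = 100/0.381 = 262.
- Maximum R²cs = 1 − exp{2[0.381 ln 0.381 + 0.619 ln 0.619]} = 0.735.
- R²cs = 0.25 × 0.735 = 0.184.
- At P = 10, S = 0.845, which agrees with the stated 0.85.

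**Parameters in joint models.**

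| Group | Three bands | With a no-injury level | Events per parameter |
|---|---|---|---|
| Medical history | 10 + 10×2 + 5 = 35 | 10 + 10×3 + 6 = 46 | 2.9 or 2.2 |
| Strength/power | 8 + 5 = 13 | 8 + 6 = 14 | 7.7 or 7.1 |
| Musculoskeletal | 5 + 5 = 10 | 5 + 6 = 11 | 10.0 or 9.1 |
| Anthropometric | 2 + 4 = 6 | 2 + 5 = 7 | 16.7 or 14.3 |

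**Benchmark shrinkage for medical history.** With the same n and R²cs, S = 0.62 at 35 parameters and 0.56 at 46. If R² is 15% to 35% instead, the ranges are 0.48 to 0.71 and 0.42 to 0.65. Reaching 0.85 at R² 25% would take about 365 events (n = 958) or 480 events (n about 1,259). Using one R² for all model sizes is an assumption.

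**One factor per model.** A count needs 1 + 5 = 6 or 1 + 6 = 7 parameters. A recency factor needs 2 + 5 = 7 or 3 + 6 = 9. That gives 100/6 = 16.7 down to 100/9 = 11.1 events per parameter, and S = 0.90 down to 0.86 at R² 25%.

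**Overlap in the joint model.** If the five muscle sites cover all recorded muscle injuries, the overall count is their sum. The intercept, five counts and total are then 7 columns of rank 6, whatever the injury rates, so those six coefficients cannot be separated. If other muscles also enter the total, the model can be estimated but is collinear. The documents give no injury rates from which to say how strongly.

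**Overlap in a one-factor model.** Write the overall count as T = H + O (hamstring plus other muscle injuries). Then a + bT + cH = a + (b + c)H + bO, so c is the hamstring effect minus the effect of other muscle injuries. If every previous muscle injury carries the same odds ratio, say an assumed 1.5, then c = 0 and the hamstring odds ratio is 1, although hamstring injury is associated with the outcome.

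**The case against.** **The joint structure is inferred.** The plan names only four adjusters, which do not include the other factors in the group. It also uses a plural for the models of a group with only two factors. Both fit one factor at a time. On that reading the parameter count and the singularity fall away. This stands, so it cannot be said that the plan commits itself to a 35- or 46-parameter model.

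**Adjusting for overall history is deliberate.** A reader might infer that a one-factor hamstring model adjusted for all muscle injuries is wrong. The documents do not support that. The stated aim is contribution beyond the developed model, and an odds ratio near 1 is the right answer if site adds nothing to the overall count. The univariable analysis reports the unadjusted association. What remains is labelling. Replacing the adjuster with other muscle injuries would change the stated target.

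**The plan does screen for collinearity.** The Model development and internal validation section describes an informal scatterplot matrix, with correlated factors dropped or combined. That screen is pairwise and may miss one variable being the sum of five others.

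**The shrinkage rule is set for model development.** This also stands: the exploratory analysis breaks no rule of the plan, and the figures here are a benchmark. By the same yardstick, one-factor models give 0.78 to 0.84 at R² 15%, so they too can miss 0.85.

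**Not every factor need fail.** A reader might infer that all 20 medical-history estimates would be unusable. Exact aliasing involves only the five counts and their total. In a simulated three-band design of 262 rows with assumed injury rates, standard errors rose about 1.4 to 1.5 times for non-muscle counts and 1.8 to 3.6 times for muscle-site counts, relative to one-factor models. With sparse rates or a fourth level, separation was frequent. How many estimates fail depends on rates that are not given.

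**Conclusion.** The point holds, conditional on the joint reading, and should be fixed before analysis. On that reading the medical-history model has 2.9 or 2.2 events per parameter at 100 events and is singular or collinear by construction. Since 100 is a minimum, the ratio may improve, but 10 events per parameter would take 350 or 460 events. Medical history is the clear outlier among the four groups. That two tenable readings differ by 35 to 46 against 6 to 9 parameters is reason enough to state the structure, even in work labelled exploratory.

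On the one-factor reading the overlap is a matter of interpretation only: an odds ratio near 1 could be taken as no association when it means no addition to overall muscle-injury history.

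A secondary wording point has wider reach. The recency bands list no level for players with no prior injury of that kind. The same bands define the recency factor in Table 2, so objective 1 is touched, as are the univariable recency estimates and the recency adjuster in all four exploratory groups. The parameter-count and overlap points, by contrast, concern only the adjusted medical-history estimates.

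**What to change.** 1. State whether the factors of a type share a model.
2. Fit each medical-history factor in its own model with the stated adjusters: 6 to 9 parameters, about 11 to 17 events per parameter. The three smaller groups may stay joint.
3. For the ten muscle-specific factors, keep the overall-history adjusters and report the odds ratio as value added over overall muscle-injury history, with a note that a value near 1 does not mean no association. A version adjusted for other muscle injuries may be added as a supplement, not as a replacement.
4. State how players with no prior injury are coded in every recency factor, including the one in Table 2.

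Cost: wording in the analysis plan, and up to 20 small models in place of one large one. The optional supplement needs a count and a recency variable for other muscle injuries at each of five sites (10 variables), derived from existing records. No new data collection is needed. The downside is that mutually adjusted estimates within the medical-history group are not reported.

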	Y Balance Test – Mean posterolateral translation**	Yes	Centimetres	Y Balance Test	Continuous	Missing data >15%
	R relative tibial angles	No	Degrees	SLS measurement with Dorsavi Viperform IMU	Continuous	Within-session ICCs=0.27-0.75 Between-session ICCs = 0.55-0.77(45)
	L relative tibial angles (left leg)	No	Degrees	SLS measurement with Dorsavi Viperform IMU	Continuous	Within-session ICCs= 0.27-0.75 Between-session ICCs = 0.55-0.77(45)
Strength/power tests	Upper body peak power difference*	Yes	Normalised watts per kilo ($W/kg^{0.67}$)	Double horizontal press using a Keiser Chest Press Air 350 machine	Continuous	Missing data > 15%
	Mean upper body peak power**	Yes	Normalised watts per kilo ($W/kg^{0.67}$)	Double horizontal press using a Keiser Chest Press Air 350 machine	Continuous	Missing data > 15%

Key: PHE=periodic health examination; WBL=weight bearing lunge; CMJ=countermovement jump; PROM=passive range of movement; ICC=intraclass correlation coefficient; SLR= straight leg raise; SLS = single leg squat; BMI= body mass index; f=force; W= watts; (note that $W/kg^{0.67}$ has a scaling factor to normalise power to body mass) Kg=kilos; IMU= inertial measurement units; m = mass; Note: composite factors are identified in the table with * denoting between limb differences and **denoting combined mean values of both limbs.

Prognostic factor exploration

Candidate PFs that were that were not selected for use in model development but not excluded, will be eligible for further exploratory analysis (Table 4). This will allow identification of other potentially useful associations which may assist future analyses or updating of the model created under the first objective of this investigation.

Table 4: Candidate prognostic factors - exploratory study

Type of prognostic factor	Candidate Prognostic factor	Composite prognostic factor	Measurement unit	Measurement method	Data type	Reliability (if applicable/available)
Anthropometric	Height	No	Centimetres	Standing height measure	Continuous	-
	Weight	No	Kilograms	Digital scales	Continuous	-
Medical history	Frequency of previous foot or ankle injuries within 3 years prior to PHE.	No	Count	Medical records	Continuous	-
	Most recent previous foot or ankle injury within 3 years prior to PHE.	No	< 6 months, 6-12 months, > 12 months	Medical records	Categorical	-
	Frequency of previous hip or groin injuries within 3 years prior to PHE.	No	Count	Medical records	Continuous	-

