	Mean hamstring muscle length /neural mobility**	Yes	Degrees	SLR using digital inclinometer	Continuous	Intra-rater ICC = 0.95-0.98.(41) Inter-rater ICC = 0.80-0.97.(41)
	Mean calf muscle length**	Yes	Degrees	WBL using digital inclinometer	Continuous	Inter-rater ICC = 0.80-0.95.(42, 43) Intra-rater ICC = 0.88.(43)
Strength/power test	Maximal loaded leg extension power difference*	Yes	Normalised watts per kilo (W/kg ^{0.67})	Double leg press test using a Keiser Air 300 machine	Continuous	Test-retest ICC = 0.886(46)
	Mean of maximal loaded leg extension power**	Yes	Normalised watts per kilo (W/kg ^{0.67})	Double leg press test using a Keiser Air 300 machine	Continuous	Test-retest ICC = 0.886(46)
	Loaded maximal leg extension velocity difference*	Yes	Peak velocity (m.s ⁻¹)	Double leg press test using a Keiser Air 300 machine	Continuous	Test-retest ICC = 0.792(46)
	Mean of maximal loaded leg extension velocity**	Yes	Peak velocity (m.s ⁻¹)	Double leg press test using a Keiser Air 300 machine	Continuous	Test-retest ICC = 0.792(46)
	Loaded maximal leg extension force difference*	Yes	Normalised peak force (N/Kg ^{0.67})	Double leg press test using a Keiser Air 300 machine	Continuous	Test-retest ICC = 0.914(46)
	Mean of maximal loaded leg extension force**	Yes	Normalised peak velocity (N/Kg ^{0.67})	Double leg press test using a Keiser Air 300 machine	Continuous	Test-retest ICC = 0.914(46)
	CMJ force per kilogram of body mass	No	Force per kg (F/kg)	CMJ using force plates	Continuous	-
	CMJ height	No	Centimetres	CMJ using force plates	Continuous	Test-retest ICC = 0.80-0.88.(47)

*Key: PF= prognostic factor; PHE=periodic health examination; WBL=weight bearing lunge; CMJ=countermovement jump; PROM=passive range of movement; ICC=intraclass correlation coefficient; SLR= straight leg raise; BMI= body mass index ;f=force; Kg=kilos; m = mass; m.s⁻¹= metres/second; Note: composite factors are identified in the table with * denoting between limb differences and **denoting combined mean values of both limbs.*

Statistical analysis

Model development and internal validation

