Multivariable logistic regression will be used for the analysis as this is an appropriate method where outcomes are binary (26) and independent variables (PFs) are continuous, categorical or a combination (36). Initially we will fit a full multivariable model containing all 10 candidate PFs to ensure a fully adjusted model prior to potential elimination of unimportant candidate factors (23). Backward elimination will then be used to successively remove non-significant factors with p-values of greater than 0.157. This threshold was set to approximate equivalence with Akaike's Information Criterion (48). Using backward elimination in this way may deliver a more parsimonious model which is therefore easier to implement in clinical practice than a full model. Where possible, we will retain continuous candidate PFs in their continuous form to avoid statistical power loss (49).

We will assume that any missing data are missing at random (MAR) so multiple imputation (MI) will be used, using 50 imputations for missing values. We have chosen to utilise MI because it avoids excluding participants from the analysis, is an effective method of handling missing prognostic factor information and can be used to account for uncertainty in missing data (50).

The apparent performance of the developed model will be summarised in the development datasets (averaged over imputation datasets), via calibration and discrimination. Model calibration determines performance in terms of the agreement between predicted outcome

risks and those actually observed (51). Graphical plots are useful to assess calibration (23), so will be produced and utilised in the analysis. We will calculate calibration-in-the-large (CITL, ideal value of 0), which quantifies the systematic error in model predictions (overall agreement). A related measure is E/O (ideal value of 1), which gives the ratio of the mean of the predicted risks against the mean of the observed risks (O) (51, 52). A calibration slope will also be calculated, where a value of 1 equals perfect calibration (26). Models demonstrate perfect calibration within development data, but in new data the slope may be <1 due to overfitting in the model development dataset (see below for how this will be handled) (52).

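### The exploratory models adjust for 4 of the 10 candidate model factors, so as planned they do not show added value over the factors in the original model

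*Combined protocol and SAP*

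**What the plan says.** Under Statistical analysis, Model development and internal validation, the original model starts from ten factors: "Initially we will fit a full multivariable model containing all 10 candidate PFs to ensure a fully adjusted model". Backward elimination then removes factors with p above 0.157, so the retained set is not known in advance. Table 2 lists the ten.

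Under Statistical analysis, Prognostic factor exploration, the Table 4 factors are grouped by type and put into logistic models that give coefficients and odds ratios "after adjustment for age, BMI, frequency of previous IMIs and most recent IMI within the 3 years prior to PHE". The protocol describes these four adjusters as factors "which were included as candidates in the original model". One exception is stated: "During multivariable analysis of the anthropometric candidate factors, BMI will not be included in these models due to collinearity with height and weight factors". The paragraph closes with "This analysis will allow examination of added prognostic value over and above other factors included in the original model".

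The methods text that introduces Table 4 says the associations found "may assist future analyses or updating of the model created under the first objective of this investigation".

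**The concern.** Added value over a model is a comparison with that model: does the factor still carry information once the model's own factors are accounted for? The planned models account for four of the ten candidates. An exploratory factor that mainly re-measures one of the other six could keep an association after the four-factor adjustment and then, on the strength of the closing sentence, be reported as adding to the model.

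What is at stake is the interpretation of the second objective and any later updating of the model that draws on it. The fitting, validation and shrinkage of the objective-1 model do not depend on this analysis.

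**Working it through.** **1. Counts.** Table 2 gives ten candidates: age, frequency of previous muscle injuries, most recent muscle injury, CMJ power, five between-limb differences (hip internal rotation, hip external rotation, hip flexor, hamstring, calf) and BMI. The adjustment set is age, BMI and the two previous-injury factors. 10 − 4 = 6 are never adjusted for: CMJ power and the five differences. Table 4 holds 2 anthropometric + 20 medical history + 5 musculoskeletal + 8 strength/power = 35 factors, which matches the protocol's own count.

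**2. Link to the final model.** Nothing makes the adjustment set follow the elimination result. Elimination could drop an adjuster and keep CMJ power. Only if all six unadjusted factors were eliminated would the four cover the final model. No likelihood-ratio comparison with the original model and no change in the C statistic is named for the exploratory models.

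**3. Where the overlap lies.** Table 4 includes CMJ height and "CMJ force per kilogram of body mass". Both come from the force-plate jump that yields CMJ power in Table 2, whose listed unit is itself a normalised peak force.

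**4. Illustrative size.** From Sample Size: at least 100 events and outcome proportion 0.381, so n = 100/0.381 ≈ 262. Assumed, because the documents give neither: the omitted factor's odds ratio per SD and its correlation r with an exploratory factor that has no effect of its own.

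- Standard error of a log odds ratio per SD: 1/√(262 × 0.381 × 0.619) = 0.127.
- Spurious log odds ratio ≈ r × ln(OR of the omitted factor).
- OR 1.5, r = 0.5: 0.5 × 0.405 = 0.203, so OR 1.22. 0.203/0.127 = 1.59, and p < 0.05 in about 36% of studies.
- OR 1.5, r = 0.7: OR 1.33, about 61%.
- OR 1.3, r = 0.5 and 0.7: about 18% and 30%.

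A logistic simulation (n = 262, 600 runs per scenario) compared the two adjustment sets:

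| Omitted OR | r | Four factors: median OR, p < 0.05 | All ten: median OR, p < 0.05 |
|---|---|---|---|
| 1.3 | 0.5 | 1.13, 16% | 1.00, 4% |
| 1.3 | 0.8 | 1.25, 37% | 1.00, 6% |
| 1.5 | 0.5 | 1.22, 32% | 1.00, 6% |
| 1.5 | 0.8 | 1.39, 67% | 1.02, 5% |

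With r = 0 (omitted OR up to 1.5) or with an omitted OR of 1.0, the four-factor rate was 3% to 6%.

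**5. Limb means against limb differences.** Cov((R + L)/2, R − L) = (Var R − Var L)/2, which is zero when the two limbs vary equally. With limb SDs 10% apart and right-left correlation 0.5 to 0.9 (assumed), the correlation of the mean with a signed difference is 0.11 to 0.21. With an omitted OR of 1.5, the formula in step 4 then gives p < 0.05 in at most about 10.5% of studies.

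**6. BMI in the anthropometric models.** Height and weight are both in that model. Under assumed squad values (height 180 cm, SD 6 to 7; weight 76 kg, SD 8 to 10; correlation 0.5 to 0.8) they explain about 99% of the variance of BMI.

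**7. Cost of fuller adjustment in the group models.** Taking 100 events, all factors of a group in one model and each categorical factor counted once, events per variable are:

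| Group | As planned | All ten factors | Linear predictor as one term |
|---|---|---|---|
| Musculoskeletal | 100/9 = 11.1 | 100/15 = 6.7 | 100/6 = 16.7 |
| Strength/power | 100/12 = 8.3 | 100/18 = 5.6 | 100/9 = 11.1 |
| Medical history | 100/24 = 4.2 | 100/30 = 3.3 | 100/21 = 4.8 |

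**The case against.** The strongest reply is that the closing sentence refers only to the four adjusters, the one set the paragraph ties to the original model, and that a small adjustment set is sensible with about 100 events. The second half stands: step 7 shows that adjusting for all ten would be costly, and the protocol names overfitting as its main constraint. The first half is a possible reading, but the sentence does not restrict itself to those four, and a reader would take it as a statement about the model.

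It can also be said that the correlation screen described before Table 2 should have removed near-duplicates. It was informal, and height, weight and BMI all came through it although the protocol later calls them collinear.

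Several stronger readings are tempting and do not hold:

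- A reader might infer that the five limb means merely repeat the five differences because they use the same measurements. Step 5 shows that they need not be appreciably correlated.
- A reader might count the anthropometric models as worse because "BMI will not be included in these models due to collinearity with height and weight factors". Step 6 shows that BMI is nearly determined by the two factors already there. The gap in that group is the same six factors.
- A reader might take 16% to 67% as the plan's false-positive rate. The correlations and odds ratios are assumed, the plan sets no p < 0.05 rule or carry-forward criterion for these factors, and factors enter by group, so the single-factor formula is only a guide.
- A reader might take model updating to be the purpose of objective 2. The protocol offers it as one possible use of an exploratory, phase 1 analysis.

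**Conclusion.** The point holds as a mismatch between a stated claim and the analysis meant to support it. The planned models estimate association adjusted for age, BMI and previous muscle injury. They do not show value over the original model's factors, unless elimination happens to remove all six unadjusted factors, a condition the plan does not state.

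The practical exposure is narrow: chiefly CMJ height and CMJ force per kilogram, and only if CMJ power is prognostic and correlated with them. Under the assumed ranges, a factor that adds nothing could show an odds ratio of about 1.13 to 1.39. If either condition fails, the distortion vanishes. The plan should be corrected because the sentence governs how objective 2 will be read, but this is a moderate point about an exploratory output.

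**What to change.** Either of two changes resolves it.

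1. **Restrict the claim.** Replace the closing sentence with a statement that the models give associations adjusted for age, BMI and previous IMI history (without BMI for height and weight), and make no added-value claim. This costs one sentence.

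2. **Keep the claim and support it.** For each of the 35 exploratory factors, fit one further logistic model per imputed dataset and pool. Include the factors retained in the objective-1 model, or that model's linear predictor as one term, plus the exploratory factor. Report the odds ratio with a pooled Wald or likelihood-ratio test, and any change in C only with optimism correction. Base the added-value statement on this analysis alone, label it exploratory, and name the retained model as the comparator. If CMJ power has been eliminated, the result does not separate the CMJ factors from it.

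With the linear predictor as a free covariate, shrinking it first changes nothing because its coefficient rescales; as an offset, the shrunken version would under-adjust. The cost of the second option is 35 short models on data already held, plus a note that the original model was estimated in the same data.
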